8.7.4 Responder Analyses

The CAPS-5 produces a Total Severity Score based on severity of PTSD symptom domains described in the DSM-5, as well as a categorical rating indicating whether a participant meets PTSD diagnostic criteria. A psychometric validation study found the following severity score ranges for the CAPS-5: Asymptomatic (0-10), Mild (11-22), Moderate (23-34), Severe (35-46), Extreme (47+). Based on these data, a 10-point reduction in CAPS-5 Total Severity Score is clinically meaningful. As an alternate definition of treatment response to assess clinical significance of study outcomes, the sponsor will conduct a responder analysis to support findings from the primary effectiveness analysis, and to explore how many single-dose treatments are needed to achieve response (See Figure 1).

[1] Response at T2, and T3 will be in comparison to Baseline at T1.

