# Medical History

- 9. At Screening, meet DSM-5 criteria for current PTSD with a symptom duration of 6 months or longer.
- 10. At Screening, have at least severe PTSD symptoms in the last month based on PCL-5 total score of 46 or greater.
- 11. May have well-controlled hypertension that has been successfully treated with antihypertensive medicines, if they pass additional screening to rule out underlying cardiovascular disease.
- 12. May have asymptomatic Hepatitis C virus (HCV) that has previously undergone evaluation and treatment as needed.
- 13. At Baseline, have a confirmed diagnosis of PTSD per CAPS-5 and at least severe symptoms in the last month constituting a CAPS-5 Total Severity Score of 35 or greater.
- 14. May have alcohol or substance use disorder if participant is not in withdrawal or requiring detox. Participants must have a plan, agreed upon by investigator, therapy team, and Medical Monitor, to reduce use of alcohol or other substances and to manage symptoms without self-medicating. Enrollment will require that, in the judgment of the investigator, therapy team, and Medical Monitor, the plan for decreasing substance use is realistic and has a good chance of succeeding in order to prevent substance use from impacting the safety or efficacy of the investigational treatment.

- 15. May have a history of or current Diabetes Mellitus (Type 2) if additional screening measures rule out underlying cardiovascular disease, if the condition is judged to be stable on effective management, and with approval by the Medical Monitor.
- 16. May have hypothyroidism if taking adequate and stable thyroid replacement medication.
- 17. May have a history of, or current, glaucoma if approval for study participation is received from an ophthalmologist.

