Treatment 1	Experimental Session 1 (Visit 5)	8 hours + overnight/ Within 1 week of Baseline CAPS-5 T1 (V3) and Preparatory Session 3 and Enrollment Confirmation (V4)  4 to 7 days after Baseline CAPS-5 T1 (V3); 1 to 4 days after Preparatory Session 3 and Enrollment Confirmation (V4). Experimental Session 1 (V5) must occur within 7 days of the Baseline CAPS-5 T1 (V3) and after Preparatory Session 3 and Enrollment Confirmation (V4)  At least 14 days after Preparatory Session 2 (V2); after Therapist Supervision Meeting	First Experimental Session is within 1 week of the Baseline CAPS-5 (V3) and 2 weeks after Preparatory Session 2 (V2); it lasts 8 hours with overnight stay. Dose is 80 mg with supplemental half-dose of 40 mg unless tolerability issues emerge with the first dose or the participant declines. Negative pregnancy test and drug test must be confirmed prior to dosing.	
Tre	Integrative Session 1.1 (Visit 6)	1.5 hours/ Morning after Experimental Session 1 (V5)  1 day after Experimental Session 1 (V5)	V6 is a 90-minute Integrative Session the morning after V5. Followed by 4 phone check-ins over the 7 days post V5.	
	Integrative Session 1.2 (Visit 7)	1.5 hours/ At least 3 days after Experimental Session 1 (V5); at least 2 days after Integrative Session 1.1 (V6); within 2 weeks after Experimental Session 1 (V5)  3 to 14 days after Experimental Session 1 (V5); at least 2 days after Integrative	Approximately 2 weeks after V5, a 90-minute Integrative Session (V7) is completed.	

CAPS-5 T2	1 hour/	Between V7 and V9, CAPS-5, SDS, and DSP-I
(Visit 8)	3 weeks (-3/+9 days) after Experimental Session 1 (V5); after Integrative Session 1.2 (V7) and before Integrative Session 1.3 (V9)	assessment completed by an IR via tele-assessment.
	18 to 30 days after Experimental Session 1 (V5); between Integrative Sessions 1.2 and 1.3 (V7 & V9) but may be same day as either.	
Integrative Session 1.3 (Visit 9)	1.5 hours/ 3 to 5 weeks after Experimental Session 1 (V5); at least 2 days after Integrative Session 1.2 (V7); may be the same day as CAPS-5 T2 (V8); 1 to 7 days before Experimental Session 2 (V10)	90-minute Integrative Session post V8 and in preparation for V10. Can occur 1 to 7 days before V10. Measures include LEC-5, PCL-5, and Since Last Visit C-SSRS.
	20 to 34 days after Experimental Session 1 (V5); at least 2 days after Integrative Session 1.2 (V7); 1 to 7 days before Experimental Session 2 (V10)	

xperimental	Visit Timing/ (Scheduling Window)	

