## Follow-up Period and Study Termination

From Integrative Session 2.3 (Visit 13) until Study Termination (Visit 15): 4 weeks (+/-2). After Integrative Session 2.3 (Visit 13), ~4 weeks with no scheduled study visits until the Primary Outcome is completed.

	Outcome is completed.				
Study Visit/		Visit Duration/	Brief Description of Events		
Visit #		Visit Timing/			
		(Scheduling Window)			
Primary Outcome	Primary Outcome CAPS-5 T3 (Visit 14)	1 hour/ ~13 (+/-3) weeks after Baseline CAPS-5 T1 (V3) & 8 weeks (+/-2) after Experimental Session 2 (V10)  67 to 112 days post Baseline CAPS-5 T1 (V3); 42 to 70 days after Experimental Session 2 (V10)	Primary Outcome CAPS-5, SDS, and DSP-I assessment completed by an IR via tele-assessment. Although there are allowable windows for all visits throughout the protocol, this visit must be completed within the overall window. Other visits should be scheduled to ensure the timing of the Primary Outcome CAPS-5 T3 assessment is appropriate.		

Termination	Study Termination (Visit 15)	2 hours ~13 (-3/+4) weeks after Baseline CAPS-5 T1 (V3) & 2 days (-1/+7 days) after Primary Outcome	Complete self-reported and safety measures; create an exit plan for participant.
erm		CAPS-5 T3 (V14)	
Study		68 to 121 days after	
$\sim$		Baseline CAPS-5 T1	
		(V3); 1 to 9 days after	
		Primary Outcome	
		CAPS-5 T3 (V14)	

Qualified IRs selected based on availability from the IR Pool will perform the CAPS-5 assessments as described Table 2.

Table 2: Primary Outcome (CAPS-5) Data Collection by Visit

CAPS Administration	Visit	Description/Timing	Target Timing Post Baseline (V3)
Baseline CAPS-5 T1	V3	Baseline; between V2 and confirmation of end of tapering and stabilization of medications	0 days
CAPS-5 T2	V8	Post Experimental Session 1 (3 weeks -3/+9 days); between Integrative Sessions 1.2 and 1.3 (V7 & V9)	~6 weeks
Primary Outcome CAPS-5 T3	V14	Post Experimental Session 2 (8 weeks +/-2) after Experimental Session 2 (V10); after Integrative Session 2.3 (V13) (4 weeks +/-2).	~13 weeks

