#### 6.1

#### Clinician-Administered PTSD Scale for DSM-5 (CAPS-5)

The last month CAPS-5 is a semi-structured interview that assesses index history of DSM-5defined traumatic event exposure [72], including the most distressing event, time since exposure, to produce a diagnostic score (presence vs. absence) and a PTSD Total Severity score [72]. The CAPS-5 rates intrusion symptoms (intrusive thoughts or memories), avoidance, cognitive and mood symptoms, arousal and reactivity symptoms, duration and degree of distress and dissociation. The CAPS-5 will be administered by a blinded IR via tele-assessment. Interviews will be conducted by the centralized remote IR pool to enhance quality control by reducing sitelevel variation in interview fidelity and quality. The IRs will be trained and supervised by senior independent raters (SIRs)fluent in the local language. Per the CAPS-5 Training Manual for the IR Pool, IRs will ensure that every single item-level score is collected in every CAPS-5 interview. The CAPS-5 is administered by the IR in a neutral, non-leading manner to minimize the chance for bias. Avoiding a biased administration can be achieved by adhering to administration guidelines verbatim and only deviating from the script to clarify, re-direct, or query further if behavioral examples are needed to determine the appropriate symptom intensity rating. Avoiding building therapeutic/clinical rapport beyond the basic level of rapport needed to conduct the interview in the research setting also minimizes the chance for bias. Remote assessment assures that the rater who is collecting the Primary Outcome will not witness Experimental Sessions and the acute effects of IP. Interviews may be recorded in as many instances as necessary to establish reliability of a random selection of interviews for accuracy. After the initial screening visit, the Irs will be blinded to visit number, number of treatments received, and any study data for the participant. IR visits will be assigned based on availability.

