## 7.3.4 Independent Rater Assessments

Participants will have one CAPS-5 assessment during the first treatment period of the study (Visits 8). An IR from the IR Pool will conduct the assessments via tele-assessment. These assessments may be recorded to establish inter-rater reliability. The results may be shared with site staff, but the IR Coordinator will enter the data. The IR will also administer the DSP-I and SDS at these time-points:

- Baseline CAPS-5 T1 (Visit 3): At least 7 days after Preparatory Session 2 (Visit 2) and confirmation of end of tapering and stabilization off medications and eligibility is confirmed.
- CAPS-5 T2 (Visit 8): 3 weeks (-3/+9 days) after Experimental Session 1 (Visit 5) or 18 to 30 days after Experimental Session 1 (Visit 5), between Integrative Session 1.2 (Visit 7) and Integrative Session 1.3 (Visit 9)
- CAPS-5 T3 (Visit 14): 8 weeks (+/-2 weeks) after Experimental Session 2 (Visit 10), after last Integrative Session 2.3 (Visit 13)

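### SAP 8.7.4 cannot show how many treatments are needed: the Visit 8 CAPS-5 looks back past the first dose, and T3 differs from T2 in more than session count

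*SAP*

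**What the plan says.** SAP 8.7.4 treats a fall of 10 points in CAPS-5 Total Severity as clinically relevant. It plans a responder analysis to support the primary result and "to explore how many single-dose treatments are needed to achieve response". Its footnote fixes the comparator: "Response at T2, and T3 will be in comparison to Baseline at T1". The section points to a Figure 1 for the detail, which is not reproduced in the text available.

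Protocol Section 6.1 describes the instrument: "The last month CAPS-5 is a semi-structured interview". Inclusion criterion 13 uses the same period ("at least severe symptoms in the last month constituting a CAPS-5 Total Severity Score of 35 or greater"). No shorter recall is described for Visit 8.

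Protocol Section 7.3.4 sets the timing of T2: "CAPS-5 T2 (Visit 8): 3 weeks (-3/+9 days) after Experimental Session 1 (Visit 5) or 18 to 30 days after Experimental Session 1". Table 1 and Table 6 of the protocol and the SAP time-and-events table give the same window. Protocol Table 1 places T3 at 42 to 70 days after Session 2.

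**The concern.** A responder rate after one session is to be set beside a rate after two, and the difference read as information about how many sessions are needed. That reading requires the two assessments to differ only in the number of sessions. They do not. A one-month recall taken about three weeks after dosing reaches back before the dose, whereas the T3 recall lies wholly after both sessions. Part of what T2 records may therefore be untreated symptoms.

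The number of sessions is a live question in the programme. Protocol Section 1.1 speaks of up to three sessions, and SAP 2.0 contrasts two sessions here with three in the sister studies. A statement in the study report that one session is often not enough could rest partly on the recall period and partly on whatever else changes between Visits 8 and 14.

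**Working it through.** **Inputs.** T2 target and window: 3 weeks, −3/+9 days after Session 1 (protocol Section 7.3.4). T3: 8 ± 2 weeks after Session 2 (protocol Table 1). Baseline (V3): 4 to 7 days before Session 1 (Table 1). Sessions 21 to 35 days apart (Table 1). Recall: one month, taken as 30 days (assumption; range 28 to 31).

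**1. Reproduce the plan's windows.**
- T2: 21 − 3 = 18 and 21 + 9 = 30 days. Agrees.
- T3: 56 − 14 = 42 and 56 + 14 = 70 days. Agrees.
- T3 after baseline: 4 + 21 + 42 = 67 and 7 + 35 + 70 = 112 days. Agrees with Table 1.

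**2. Pre-dose share of the recall period.** Share = max(0, L − d)/L, with L recall days and d days since the session.

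| Day of assessment | L = 28 | L = 30 | L = 31 |
|---|---|---|---|
| T2, day 18 | 10/28 = 36% | 12/30 = 40% | 13/31 = 42% |
| T2, day 21 (target) | 7/28 = 25% | 9/30 = 30% | 10/31 = 32% |
| T2, day 24 | 4/28 = 14% | 6/30 = 20% | 7/31 = 23% |
| T2, day 30 | 0% | 0% | 1/31 = 3% |
| T3, day 42 (earliest) | 0% | 0% | 0% |

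If Visit 8 were spread evenly over days 18 to 30 (assumption), the average share on a 30-day month would be 20%.

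**3. Overlap with baseline.** At day 18 the recall reaches 12 days before Session 1. Baseline is 4 to 7 days before it, so 12 − 7 = 5 to 12 − 4 = 8 of those days were also rated at T1.

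**4. What else differs between T2 and T3.**
- Elapsed time: T2 is 4 + 18 = 22 to 7 + 30 = 37 days after baseline; T3 is 67 to 112.
- Therapy: V9, V11, V12 and V13 normally fall between them, which is four integrative sessions. Visit 8 may share a day with V7 or V9, hence ‘normally’.
- Dose: the initial dose is 80 mg in Session 1 and 80 or 120 mg in Session 2.

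**5. The T2 target in protocol Table 2.** That table gives about six weeks after baseline. Six weeks is 42 days, or 42 − 7 = 35 to 42 − 4 = 38 days after Session 1. The Visit 8 window ends at day 30, V9 must fall by day 34, and Session 2 by day 35. Visit 8 may not follow V9, so the target cannot be met together with these windows.

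**The case against.** **The instrument may not behave as an average.** Nothing in the documents says that a CAPS-5 score weights each day of the month equally. Section 6.1 describes interviewer ratings of symptom intensity and refers to a training manual that is not in hand. This stands: the direction is conditional, and the size is unknown. A reader might turn the shares above into a shortfall in the response rate. That would need an averaging model and a mean and SD of change, none of which the documents give.

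**The 40% is an edge case.** It applies at day 18 of a window that extends further late than early. This also stands, but the overlap at the target day is still 30%.

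**Table 2 implies a later T2 with no overlap.** This does not stand, because a visit at six weeks cannot be fitted to the V8, V9 and V10 windows.

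**The net direction is open.** T3 is six to ten weeks after dosing, and any waning of effect would lower T3 response. This is fair. It is another reason why the contrast cannot isolate the number of sessions.

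**The responder definition is not fully visible.** Figure 1 is missing from the available text, so whether the same 10-point cut applies at both visits could not be confirmed. The recall overlap does not depend on the cut.

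**The analysis is exploratory, and response by visit is already what the footnote reports.** True, and this limits the remedy to the stated aim and its interpretation. A reader might also infer that these rates will set the number of Phase 3 sessions. No section says so; the documents speak of validating power assumptions and confirming the Phase 3 design.

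**Conclusion.** The point holds as a limit on interpretation. On a 30-day month, the T2 recall contains 30% pre-dose days at the target visit, between 0% and 40% across the window, and T3 contains none. If pre-dose days enter the rating and symptoms fall after Session 1, this overlap lowers T2 response relative to T3. The shares rest on the documents' windows plus the length of a month; the effect on response rates cannot be derived from them. Apart from recall, elapsed time, further integrative sessions and a possible dose increase are all tied to visit in this single-arm sequence. The T2–T3 difference therefore cannot be read as the number of treatments needed.

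The analysis is supportive, and the change is desirable rather than essential. The primary endpoint at T3 is not affected. The same caution applies to the T2 point in the onset plots of SAP 8.7.

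**What to change.** In SAP 8.7.4:
- replace the aim about the number of treatments needed with response by visit, at T2 and at T3, each against T1;
- state that the T2 recall period partly precedes dosing, and that the T2–T3 difference is not to be read as the number of treatments needed;
- tabulate T2 response descriptively with days from Session 1 to Visit 8.

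A covariate adjustment for days to Visit 8 is not recommended, because it cannot separate recall dilution from real improvement over time. Nor is a subset seen at day 28 or later: it would be very small and would still carry up to 2/30 pre-dose days.

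Separately, reconcile the T2 target in protocol Table 2 (and its synopsis counterpart) with the 18 to 30 day window.

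The cost is SAP wording, one descriptive table from the visit dates, and the loss of one exploratory claim. No visit or procedure needs to change for the SAP edits.

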8.8 Safety Analyses

Safety assessment analyses for this study will include summaries of unsolicited adverse events, concomitant medications, suicidal ideation and behavior, and vital signs. Qualitative safety analyses will examine safety data with summary tables listing drug exposure, concomitant medications/therapies, unsolicited AEs, and percentages tabulated overall.

8.8.1 Analysis of Exposure

The frequencies and percentages of participants with exposure will be summarized. Data will be tabulated for the Safety Set.

8.8.2 Analysis of Adverse Events

The primary measure of safety will be the reporting of unsolicited AEs. All AEs collected from Enrollment to Termination will be categorized as follows:

- Pretreatment AEs are defined as AEs that occur during the Preparatory Period prior to the first dose in the first Experimental Session
- Treatment Emergent AEs are defined as AEs that occur during the Treatment Period from the first Experimental Session to the last Integrative Session
- AEs that occur on and two days after MDMA or placebo administration
- AESIs are defined as AEs specified in the protocol related to cardiac function and abuse liability
- Follow-up Period AEs are defined as AEs that occur during the Follow-up Period after the last Integrative Session through Termination
- AEs leading to discontinuation of IP
- AEs resulting in death or hospitalization.
- SAEs
- AEs continuing at Termination.

Verbatim terms on case report forms will be mapped to preferred terms (PT) and system organ class (SOC) using the Medical Dictionary for Regulatory Activities (MedDRA) Version 20.0 (Hierarchy), WHO DRUG Enhanced Mar-2018 B3 (Hierarchy and Ingredients).

Frequency and incidence of AEs will be displayed by PT, sorted by SOC, and summarized by treatment group, analysis set, category (as defined above), severity, and seriousness. AEs will be analyzed and presented as follows:

- If a participant has more than one AE mapped to the same PT, that AE will be reported once using the highest severity
- Relationship will be determined based on relative incidence of TEAEs with at least twofold difference between MDMA vs. placebo
- Compare relative incidence of AEs during Experimental Sessions such as clinical signs and symptoms, such as chest pain, shortness of breath, or neurological symptoms or any other signs or symptoms that may be indicative of a medical complication of the investigational product
- AEs that occur on day of Experimental Sessions and two days after IP administration will be presented separately.

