Stud	ly Visit/	Visit Duration/	Brief Description of Events
Visi	t #	Visit Timing/	
		(Scheduling Window)	
Treatment 2	Experimental Session 2 (Visit 10)	8 hours + overnight/ 3 to 5 weeks after Experimental Session 1 (V5); at least 2 weeks after Integrative Session 1.3 (V9)  21 to 35 days after Experimental Session 1 (V5)  At least 14 days after Integrative Session 1.2 (V7); after Therapist Supervision Meeting	3 to 5 weeks after V5, and 2 weeks after Integrative Session 1.1 (V6). The second Experimental Session lasts 8 hours with an overnight stay. Dose is 80 or 120 mg plus supplemental half-dose (80 mg + supplemental 40 mg -OR- 120 mg + supplemental 60 mg) unless tolerability issues emerge with the first dose or the participant declines. Negative pregnancy test and drug test must be confirmed prior to dosing.

Integrative Session 2.1 (Visit 11)	1.5 hours/ Morning after Experimental Session 2 (V10)  1 day after Experimental Session 2 (V10)	V11 is a 90-minute Integrative Session the morning after V10. Followed by 4 phone check-ins over 7 days post V10.
Integrative Session 2.2 (Visit 12)	1.5 hours/ At least 3 days after Experimental Session 2 (V10); at least 2 days after Integrative Session 2.1 (V11); within 2 weeks after Experimental Session 2 (V10)  3 to 14 days after Experimental session 2	Approximately 2 weeks after V10, a 90-minute Integrative Session (V12) is completed.
	(V10); at least 2 days after Integrative Session 2.1 (V11)	
Integrative Session 2.3 (Visit 13)	1.5 hours/ 3 to 5 weeks after Experimental Session 2 (V10)	90-minute Integrative Session post V12. Measures include LEC-5, PCL-5 and Since Last Visit C-SSRS.
	20 to 34 days after Experimental Session 2 (V10); at least 2 days after Integrative Session 2.2 (V12)	

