# **Safety Objectives**

The overall safety objective is to assess severity, incidence and frequency of AEs, AEs of Special Interest (AESIs), and Serious Adverse Events (SAEs), concomitant medication use, suicidal ideation and behavior, and vital signs to support the package insert for MDMA-assisted psychotherapy. The following safety objectives will evaluate the safety of MDMA-assisted psychotherapy:

- 1. Assess incidence of AEs during Experimental Sessions that may be indicative of a medical complication of the Investigational Product (IP), such as clinical signs and symptoms of chest pain, shortness of breath, or neurological symptoms or any other signs or symptoms that prompt additional vital sign measurements.
- 2. Assess incidence of AEs by severity.
- 3. Assess incidence of Treatment Emergent AEs (TEAEs) by severity.
- 4. Assess incidence of TEAEs by severity taken during an Experimental Session and through 2 days after IP administration.
- 5. Assess incidence of AESIs, defined as AEs specified in the protocol related to cardiac function and abuse liability.
- 6. Assess incidence of AEs by severity categorized as leading to discontinuation of IP, resulting in death or hospitalization, and continuing at Study Termination.
- 7. Assess incidence of SAEs.
- 8. Assess incidence of psychiatric concomitant medications taken during an Experimental Session and through 2 days after IP administration.
- 9. Assess incidence of any psychiatric concomitant medications taken during the Treatment Period.
- 10. Assess incidence of serious suicidal ideation and positive suicidal behavior assessed with the Columbia Suicide Severity Rating Scale (C-SSRS).
- 11. Assess mean changes in blood pressure, heart rate, and body temperature from pre-IP administration to end of each Experimental Session.

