## 10.1.1 Adverse Events of Special Interest

The sponsor will pay special attention to a subset of AEs involving psychological distress, including Low Mood (occurring up to 5 days after Experimental Sessions), suicidal ideation and suicidal behavior, as well as cardiac function that could be indicative of QT interval prolongation or cardiac arrhythmias, including Torsade de pointes, sudden death, ventricular extrasystoles, ventricular tachycardia, ventricular fibrillation and flutter, syncope (non-postural), and seizures. These AEs will be marked in the eCRF with the denotation "Adverse Event of Special Interest" (AESIs) whether serious or non-serious.

In order to assess signals of abuse potential for the IP in the intended patient population:

- AESIs involving the terms of Behavioral addiction, Drug abuser, Substance abuser, Dependence, Intentional product misuse (including facilitation of product use outside of research setting), Overdose (accidental, intentional, or prescribed), or Drug diversion will be collected and coded as AESIs in the eCRF if noted in relation to MDMA or Ecstasy.
- Cases of noncompliance, protocol violations, participants lost to follow-up, and any other reasons why participants dropped out of the study will be assessed for presence of AESIs.
- Qualitative urine drug test data will be collected prior to each Experimental Session. Any
  positive findings that cannot be attributed to pre-approved concomitant medications or
  diet will be reviewed by the Medical Monitor to assess compliance with ongoing
  eligibility criteria and for presence of AESIs.

If an AESI is a SAE, it should be reported via the eCRF within 24 hours of the site's awareness of the event.

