8.4 Baseline Values

Baseline values are from Baseline Visits for all measures, except C-SSRS, AUDIT, DUDIT, resting blood pressure (BP), Body Mass Index (BMI). For C-SSRS, the initial screening visit will be conducted with the 'Lifetime' version of the measure. The Independent Rater Screening assessment of 'Since Last Visit' suicidal ideation and behavior will be used as 'Baseline.' For the AUDIT and DUDIT measures and resting BP, BMI, results collected at Screening will be used as the Baseline value.

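### The SAP's AESI category leaves out one of the protocol's three AESI groups: Low Mood, suicidal ideation and suicidal behavior

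*SAP*

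**What the plan says.** Protocol 10.1.1 opens its AESI list with "a subset of AEs involving psychological distress, including Low Mood (occurring up to 5 days after Experimental Sessions), suicidal ideation and suicidal behavior". It goes on to cardiac events that could point to QT prolongation or arrhythmia, and continues: "These AEs will be marked in the eCRF with the denotation" of an AESI, whether or not the event is serious. A further list covers abuse, misuse, overdose and diversion in relation to MDMA or Ecstasy, also coded as AESIs in the eCRF.

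The protocol's own safety objective 5, in the Synopsis and in section 2.3, is narrower: "Assess incidence of AESIs, defined as AEs specified in the protocol related to cardiac function and abuse liability". SAP 3.3 repeats that objective, and the analysis category in SAP 8.8.2 says the same: "AESIs are defined as AEs specified in the protocol related to cardiac function and abuse liability". SAP 8.8.2 then has AEs "summarized by treatment group, analysis set, category (as defined above), severity, and seriousness".

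On the C-SSRS, SAP 8.4 exempts the scale from the general baseline rule and names the Independent Rater Screening form as its baseline. SAP 8.8.4 tabulates results by period. The periods before the first session are lifetime, screening and baseline.

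**The concern.** Sites are told to flag three groups of events, while the analysis category describes two. A programmer who follows the SAP would drop events that the site marked as AESIs, and the reported AESI count would then disagree with the eCRF. AESI incidence is a stated safety objective, and both documents say the safety objectives are meant to support the package insert.

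Low Mood is the most exposed event type. Suicidality has its own C-SSRS summary; Low Mood has no dedicated summary elsewhere. The BDI-II does not fill the gap, because it is given only at Visits 4 and 15 (protocol Table 7). Protocol 9.2.2.2 itself notes that depressed mood is sometimes reported 1 to 3 days after MDMA, so such events are to be expected.

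**Working it through.** No power or sample size figure bears on this point. The check compares the texts and counts days.

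**1. AESI groups by place**

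| Place | Psychological distress | Cardiac function | Abuse |
|---|---|---|---|
| Protocol 10.1.1 | yes (3 named event types) | yes | yes |
| Protocol Synopsis, Safety Objectives, item 5 | no | yes | yes |
| Protocol 2.3, item 5 | no | yes | yes |
| SAP 3.3, item 5 | no | yes | yes |
| SAP 8.8.2 | no | yes | yes |

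Groups missing from SAP 8.8.2: 3 − 2 = 1. The two-group wording stands in 4 places. Two of these are in the protocol, so the SAP inherits the conflict.

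**2. Effect on the table.** SAP 8.8.2 summarizes AEs by the categories it has just defined. Taken literally, a Low Mood or suicidal ideation event flagged under protocol 10.1.1 does not enter the AESI category.

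**3. Where Low Mood then appears.** Count the session day as Day 0.

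- Protocol window: up to Day 5.
- Separate acute presentation in SAP 8.8.2: session day plus two days, so Days 0 to 2.
- Outside it: Days 3, 4 and 5, that is 5 − 2 = 3 days.
- Treatment-emergent category: "AEs that occur during the Treatment Period from the first Experimental Session to the last Integrative Session". Visit 13, the last planned Integrative Session, is 20 to 34 days after session 2. The earliest date is Day 20, and 20 − 5 = 15 days after the Low Mood window closes. For a participant who keeps the Integrative Session schedule, all of Days 0 to 5 after either session is therefore treatment-emergent.
- For a participant who attends no Integrative Session after Visit 6 or Visit 11 (Day 1), the last session attended is on Day 1. Low Mood on Days 2 to 5 may then be classed as a follow-up AE. SAP 8.8.2 does not say whether the last session means the last planned or the last attended.

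**4. C-SSRS rows before the first session**

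| Form | Relation to taper | Row in SAP 8.8.4 |
|---|---|---|
| Site screening, Lifetime version | before | lifetime |
| Rater screening, Since Last Visit | before (taper starts at Visit 0) | baseline, by SAP 8.4 |
| Visit 4, Since Last Visit | after | none clear |

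The label *screening* is left unexplained; the Lifetime form, given at the initial screening visit, might be meant to fill it as well. Visit 4 has no evident row, although protocol 6.3 plans the C-SSRS both before and after washout for participants who stop medication.

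**The case against.** The SAP sentence refers to AEs that the protocol specifies, which points back to 10.1.1, and the eCRF carries the flag. A programmer could build the table from the flag and get the full count. That is fair as far as it goes: the SAP does not say whether the flag or the sentence governs, so the omission is conditional on following the sentence. But the same sentence limits AESIs to two groups. Two defensible programs would give different counts for one safety objective, and that is the defect.

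It is also true that little information disappears. Every AE is displayed by preferred term and system organ class, Days 0 to 2 are shown separately, and suicidality is tabulated from the C-SSRS. This limits the point to the AESI count, in a single-arm study of up to 40 participants.

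Three stronger readings are tempting, and the documents do not support them:

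- *The C-SSRS baseline is undefined, or could be taken before or after taper.* SAP 8.4 settles it as the rater-screening form. A Baseline column heading over Visit 4 does not override a specific definition. SAP 8.8.4 plans counts and percentages by period and no comparison with baseline, so no biased contrast follows.
- *Low Mood on Days 0 to 5 is always captured as treatment-emergent.* That holds only for participants who keep the Integrative Session schedule.
- *The vital-sign plan misses the peak effect.* Objective 11 measures change only to session end, but SAP 8.8.5 already tabulates the reading before the supplemental dose. The peak time in protocol 1.2.2 describes MDMA effects in general and is not given for blood pressure, pulse or temperature.

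**Conclusion.** The inconsistency is real and should be corrected. Protocol 10.1.1 sets three AESI groups; objective 5 in both documents and SAP 8.8.2 name two. If the table follows the SAP sentence, 1 of 3 groups is left out. The documents give no expected incidence, so the number of events affected cannot be estimated. The loss is in classification and in the accuracy of the AESI count, chiefly for Low Mood. It is not a loss of data.

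The C-SSRS matter is a mismatch of row labels between SAP 8.4 and 8.8.4 and needs only a clarification. The vital-sign change is an optional addition and does not correct an error.

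**What to change.** 1. Replace the two-group wording in objective 5 (protocol Synopsis, protocol 2.3, SAP 3.3) and in SAP 8.8.2 with a reference to the AESI list in protocol 10.1.1. State in SAP 8.8.2 that the AESI table is built from the eCRF flag.
2. Minor: cite SAP 8.4 in SAP 8.8.4, say which form fills the screening label, and show Visit 4 as its own pre-dose row.
3. Optional: in SAP 8.8.5, add the within-participant change from the pre-dose reading to the reading before the supplemental dose.

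The cost is one line in each of the four AESI places, a sentence or two in SAP 8.8.4, one table row and, if wanted, one column. The two protocol lines need a protocol amendment; the SAP text can be revised on its own. All the data involved are already scheduled for collection.
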